3.4. Baseline Variables

Baseline characteristics will be collected according to the schedule of activities (SoA) as specified in the protocol.

3.5. Safety Endpoints

The following data are considered in standard safety summaries (see protocol for collection days, baseline assessment, and list of parameters):

- adverse events (AE)
- laboratory data
- body weight
- mental health
- vital signs data
- electrocardiogram (ECG) results

3.5.1. Adverse Events

Any adverse events occurring following start of treatment will be considered as treatment emergent adverse event (TEAE). Events that occur during follow-up within the lag time of up to 35 days after the last dose of study intervention will be counted as treatment emergent and attributed to the last treatment taken. The time period for collecting AEs (“active collection period”) for each participant begins from the time the participant provides informed consent.

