2.2. Study Objectives and Endpoints

Objectives	Endpoints
Primary:	Primary:

 • To estimate the effect of MD itraconazole on the single-dose PK of PF-07081532 in otherwise healthy, overweight or obese participants. • To estimate the effect of SD cyclosporine on the single-dose PK of PF-07081532 in otherwise healthy, overweight or obese participants. 	
 • PF-07081532 PK parameter: AUC_{inf}(if data permit^a otherwise AUC_{last}) • PF-07081532 PK parameter: AUC_{inf}(if data permit^a otherwise AUC_{last})
Secondary:	Secondary:

 • To evaluate the safety and tolerability of PF-07081532 administered separately and in combination with itraconazole or cyclosporine in otherwise healthy, overweight or obese participants. • To evaluate the effects of itraconazole or cyclosporine on additional PK parameters for PF-07081532. 	
 • Assessment of TEAEs, clinical laboratory abnormalities, vital signs, body weight, and ECG parameters. • Assessment of mental health as determined by C-SSRS and PHQ-9. • Additional plasma PK parameters for PF-07081532: C_{max} and T_{max}; and CL/F, V_z/F, $t_{1/2}$, as data permit.

a. Should it be deemed that too few AUC_{inf} estimates (eg, less than 12 for a single treatment) are obtained from the evaluable participants, AUC_{last} may be selected as the primary endpoint for CSR reporting.

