2.3. Study Design

This is a Phase 1, open-label, fixed-sequence, 3-period study to evaluate the effect of multiple doses of itraconazole and a single dose of cyclosporine on the single-dose PK of PF-07081532 in otherwise healthy, overweight or obese adult participants. The 3 study periods will be conducted consecutively without a break.

All participants will provide informed consent and undergo Screening evaluations to determine their eligibility. Screening will occur within 28 days of the first dose of study intervention on Period 1 Day 1. Participants who discontinue from the study before completing all assessments may be replaced at the discretion of the investigator and sponsor.

Approximately 16 participants will be enrolled in the study such that approximately 12 evaluable participants complete the study.

The total duration of participation from the Screening Visit to the F/U telephone contact will be approximately 82 days or 12 weeks, approximately 3 weeks of which will be conducted on an inpatient basis. The 21-day inpatient portion of the study will be conducted as follows:

Period 1: Days -1 to 5 (Study Days -1 to 5; participants are admitted to the CRU on Day -1), 40 mg SD PF-07081532 on Day 1;

Period 2: Days 1 to 5 (Study Days 6 to 10), 40 mg SD PF-07081532 plus 600 mg SD cyclosporine on Day 1;

Period 3: Days 1 to 10 (Study Days 11 to 20; participants are discharged from the CRU on Study Day 20), 200 mg itraconazole QD × 9 days plus 40 mg SD PF-07081532 on Day 4.

A telephone F/U contact will occur 28-35 days from the last dose of study intervention (Period 3, Day 9).

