6.5.1. Adverse Events

Adverse events will be reported in accordance with the CaPS.

Participant discontinuations due to adverse events will be detailed by treatment. Data will be reported in accordance with the CaPS.

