Appendix 1. SAS Code for Analyses

An example of the PROC MIXED code is provided below:

For the primary objective:

Treatment B (Test) vs Treatment A (Reference)

```
proc mixed data=tab.pk;
  where trt in ("A","B");
  class trt participant;
  model l&var=trt / ddfm=KR;
  random participant / subject=participant;
  lsmeans trt;
  estimate 'B vs A' trt -1 1 /cl alpha=0.1;

  ods 'Estimates' out=est&var;
  ods 'lsmeans' out=ls&var;
  ods 'covparms' out=cov&var;
  ods 'tests3' out=tst&var;
run;
```

Treatment C (Test) vs Treatment A (Reference)

```
proc mixed data=tab.pk;
  where trt in ("A","C");
  class trt participant;
  model l&var=trt / ddfm=KR;
  random participant / subject=participant;
  lsmeans trt;
  estimate 'C vs A' trt -1 1 /cl alpha=0.1;

  ods 'Estimates' out=est&var;
  ods 'lsmeans' out=ls&var;
  ods 'covparms' out=cov&var;
  ods 'tests3' out=tst&var;
run;
```

```
/* Letter assignments for treatments (trt) within the estimate statement above are as follows
A: 40 mg SD PF-07081532
B: 40 mg SD PF-07081532 plus 600 mg SD cyclosporine
C: 200 mg itraconazole QD x9 days plus 40 mg SD PF-07081532
*/
```

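### Under the SAP's attribution rule, participants who complete the study carry 37-44 adverse-event days on the itraconazole combination against 5 on each other treatment, and no equal-window summary is specified

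*SAP*

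**What the plan says.** SAP 3.5.1 treats any event after the start of treatment as treatment emergent. Events in follow-up, up to 35 days after the last dose, are "counted as treatment emergent and attributed to the last treatment taken".

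The calendar is in SAP 2.3, and the periods run on without a gap:

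- In the first period PF-07081532 is given alone on Study Day 1, and the period closes on Study Day 5.
- In the second, PF-07081532 and cyclosporine are given together on Study Day 6, and the period closes on Study Day 10.
- The third occupies Study Days 11 to 20. Itraconazole is given once daily for nine days, "plus 40 mg SD PF-07081532 on Day 4".

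The follow-up phone call is 28-35 days after the last itraconazole dose.

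The relevant secondary objective is the safety of PF-07081532 "administered separately and in combination with itraconazole or cyclosporine". On presentation, SAP 6.5.1 refers to the sponsor's reporting standard (CaPS) and adds: "Participant discontinuations due to adverse events will be detailed by treatment". Neither 3.5.1 nor 6.5.1 mentions a common window, an exposure-adjusted rate, or a separate category for the itraconazole lead-in or for follow-up.

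The only place that gives the treatments letters is the code comment in SAP Appendix 1, which reads "C: 200 mg itraconazole QD x9 days plus 40 mg SD PF-07081532". No itraconazole-alone category is defined.

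**The concern.** An attribution rule matters only if events are shown by treatment, and the secondary objective calls for that view. Here the rule gives one treatment a much longer time at risk than the other two. Because every participant has the same order, follow-up time cannot balance out across treatments. A reader of a by-treatment table could take a difference in observation time for an effect of itraconazole on tolerability.

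The second issue is the lead-in. On Period 3 Days 1-3 only itraconazole is dosed, and the SAP does not say where an event on those days belongs. If it is placed under the combination, it is credited to a pairing the participant has not yet received in that period. That sits badly with the safety set's principle, in SAP section 4, of analysing people by what they actually took.

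**Working it through.** **Inputs.** Period calendar and dosing days: SAP 2.3. Last dose on Study Day 19 and phone contact on Study Days 47-54: Protocol Table 1. Attribution rule: SAP 3.5.1.

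**Reproducing the plan's calendar.** 19 + 28 = 47 and 19 + 35 = 54, which matches the schedule. 28 screening days + 54 = 82 days, the stated total. Day -1 plus Study Days 1-20 = 21 inpatient days, also as stated.

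**Windows for a participant who completes all periods (inclusive calendar days).**

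- A (PF-07081532 alone): Study Days 1-5 = 5.
- B (with cyclosporine): Study Days 6-10 = 5.
- C (with itraconazole): Study Day 11 to 47 = 37, or to 54 = 44.
- Ratio: 37/5 = 7.4 to 44/5 = 8.8.

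Of the C days, 3 (Study Days 11-13) precede the PF-07081532 dose on Study Day 14, and 28-35 follow the last itraconazole dose.

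**If the lead-in were assigned to B instead.** A = 5, B = 8 (Study Days 6-13), C = 34-41 (Study Day 14 to 47-54). The windows remain unequal.

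**Participants who stop early.** Someone whose last dose is on Day 1 of Period 1 or 2 is followed to 28-35 days after it. That is 1 + 28 = 29 to 1 + 35 = 36 inclusive days, all under A or B.

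**Illustration of size.** The documents give no background event rate, so the rate r per participant-day is an assumption, taken as constant. P(at least one event) = 1 - exp(-r x days).

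| Assumed r | 5 days (A or B) | 37 days (C) | 44 days (C) |
|---|---|---|---|
| 0.002 | 1.0% | 7.1% | 8.4% |
| 0.01 | 4.9% | 30.9% | 35.6% |
| 0.05 | 22.1% | 84.3% | 88.9% |

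At r = 0.01 with 12 participants, the expected number with an event is 12 x 0.049 = 0.6 against 12 x 0.309 = 3.7 to 12 x 0.356 = 4.3.

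**If nothing were detected after discharge.** C would still hold 10 days (Study Days 11-20), or 7 without the lead-in (Study Days 14-20). At r = 0.01 that gives 1 - exp(-0.10) = 9.5% or 1 - exp(-0.07) = 6.8%, against 4.9%. Under a constant rate the direction stays the same, but the gap is far smaller.

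**Is the lead-in free of PF-07081532?** Using the mean half-lives in Protocol 2.2.4.1 (18.03 to 26.50 h), the fraction left 120 h after the Period 2 dose is 2^(-120/18.03) = 1.0% to 2^(-120/26.50) = 4.3%, before any cyclosporine effect. Itraconazole-only therefore describes the dosing and does not mean zero exposure.

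**The case against.** Several objections have force and limit the claim.

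- **The lead-in.** A reader might infer that SAP 3.5.1 itself assigns Period 3 Days 1-3 to the combination. It does not: the quoted rule covers follow-up only, and the treatment label in Appendix 1 is a comment in the PK model code. The period and treatment definitions suggest those days fall under C, but what the documents show is an absent rule.
- **Who ends on C.** A reader might infer that all follow-up goes to C. The plan enrols about 16 to obtain about 12 evaluable completers, and those who stop early carry follow-up under A or B.
- **The table is not visible.** The CaPS layout is not in the documents, and only discontinuations due to adverse events are expressly by treatment. The standard may already separate these windows.
- **Constant rate.** After discharge the only scheduled contact is one phone call, so detection per day is probably lower than in the unit. Drug-related events may also cluster after dosing. The illustrated percentages could be well off.
- **Role of the summary.** Safety is descriptive, no hypothesis is tested, and investigators judge causality event by event, so interpretation does not rest on crude percentages alone.

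None of this removes the core. The follow-up rule is explicit, the windows for completers follow from the calendar, and nothing in the SAP offsets the imbalance. Unequal detection is a further reason not to merge inpatient and follow-up events in one column.

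**Conclusion.** The point holds in a limited form. For participants who complete all periods, the adverse-event windows are 5, 5 and 37-44 calendar days, a 7.4- to 8.8-fold difference that comes from the schedule and the attribution rule. Crude by-treatment TEAE incidence under that rule would therefore tend to be higher for the itraconazole combination with no drug effect. The 4.9% versus 30.9-35.6% comparison depends on an assumed constant rate of 0.01 per participant-day and equal detection throughout.

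The stronger statement, that the table is bound to show more events with itraconazole, is not supported: the layout is unseen, the rate is unknown, and follow-up detection may be weaker. For Period 3 Days 1-3 the finding is that the SAP is silent.

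The effect is confined to the descriptive secondary safety summary. The primary AUC analyses are not touched.

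**What to change.** Keep the overall TEAE definition and the last-treatment table. In SAP 3.5.1 and 6.5.1, add one by-treatment TEAE table with these columns:

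- A, B and C, each limited to onset within 120 h after that period's PF-07081532 dose. In Periods 1 and 2, 120 h ends where the next period starts (Study Day 1 + 5 = 6; 6 + 5 = 11), so the windows do not overlap.
- Period 3 Days 1-3, before the PF-07081532 dose, footnoted for possible residual effect of Period 2.
- Events after 120 h in Period 3 or in follow-up.

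If only onset dates are available, Study Days 1-5, 6-10 and 14-18 give the same equal lengths. If CaPS already separates these windows, a sentence in the SAP saying so is enough.

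The cost is a short SAP revision and one extra table. Dose times are already recorded (Protocol 6.5) and adverse events are already collected throughout, so no new data are needed. There are limits: late-onset combination events fall outside the equal-window comparison, although PK sampling in Period 3 runs to 144 h. A late event after the cyclosporine period would appear in the lead-in column, hence the footnote. Fixed order and carry-over remain. The change should be made before the adverse-event tables are produced.

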3.5.2. Laboratory Data

Safety laboratory tests will be performed as described in the protocol. To determine if there are any clinically significant laboratory abnormalities, the hematological, clinical chemistry (serum) and urinalysis safety tests will be assessed against the criteria specified in the sponsor’s reporting standards. The assessment will not take into account whether each participant’s baseline test result is within or outside the laboratory reference range for the particular laboratory parameter.

The baseline measurement is the latest predose measurement on Day 1 of Period 1.

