**Table 1. Study Schedule of Assessment**

Visit Identifier' Abbreviations used in this table may be found in Annex 9 .	Screen	Period 1		Period 2	Period 3	F/U (Phone Call)	ET	Notes
Study Day		-1	to 5	6 to 10	11 to 20	28 to 54		
Days Relative to Day 1	D-28 to D-2	D-1	D1 to D5	D1 to D5	D1 to D10	28-35 Days		1. All screening should be done 28 days before the first dose. 2. Day relative to start of study intervention (Day 1). 3. In this study, follow-up is to be conducted via phone contact 28 to 35 days after administration of the final dose of study intervention (Period 3 Day 9, Study Day 19).
Safety laboratory (hematology, chemistry, and UA)	X	X		X (D5 chemistry only)	X		X	
 
See Table 5 for a complete list of clinical lab tests.
 
Period 3 collection prior to discharge on Day 10.
 

Calcitonin, amylase, lipase, HbA1C, TSH, C-Peptide	X							
 
An overnight fast is required prior to calcitonin sample collection.
 

Demography	X							
 
Including height and weight.
 

Serum and urine pregnancy test (WOCBP only)	X	X			X (D10)		X	
 
Pregnancy tests will also be done whenever 1 menstrual cycle is missed during the active treatment period (or when potential pregnancy is otherwise suspected) and at the end of the study prior to discharge on Period 3 Day 10.
 

Contraception check	X	X				X	X	
FSH	X							
 
For any female who has been amenorrheic for at least 12 consecutive months.
 

Urine drug testing	X	X						
 
Participants may undergo random urine drug testing at the discretion of the investigator.
 

Single 12-Lead ECG	X		X	X	X		X	
 
Pre-dose Day 1 in each period, and prior to discharge on Period 3 Day 10.
 

Blood pressure, pulse rate, and body temperature	X		X	X	X		X	
 
Pre-dose Day 1 in each period, and prior to discharge on Period 3 Day 10.
 
Body temperature will be taken at Screening only.
 

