## 3. OBJECTIVES AND ENDPOINTS

Objectives	Endpoints
Primary:	Primary:

 
To estimate the effect of MD itraconazole on the single-dose PK of PF-07081532 in otherwise healthy, overweight or obese participants.
 
	
 
PF-07081532 PK parameter: AUCinf (if data permita otherwise AUClast)
 

 
To estimate the effect of SD cyclosporine on the single-dose PK of PF-07081532 in otherwise healthy, overweight or obese participants.
 
	
 
PF-07081532 PK parameter: AUCinf (if data permita otherwise AUClast)
 

Secondary:	Secondary:

 
To evaluate the safety and tolerability of PF-07081532 administered separately and in combination with itraconazole or cyclosporine in otherwise healthy, overweight or obese participants.
 
	
 
Assessment of TEAEs, clinical laboratory abnormalities, vital signs, body weight, and ECG parameters.
 
Assessment of mental health as determined by C-SSRS and PHQ-9.
 

 
To evaluate the effects of itraconazole or cyclosporine on additional PK parameters for PF-07081532.
 
	
 
Additional plasma PK parameters for PF-07081532: Cmax and Tmax; and CL/F, Vz/F, t1/2, as data permit.
 

a. Should it be deemed that too few AUCinf estimates (eg, less than 12 for a single treatment) are obtained from the evaluable participants, AUClast may be selected as the primary endpoint for CSR reporting.

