### 4.2. Scientific Rationale for Study Design

The purpose of this study is to characterize the effect of multiple doses of itraconazole and a single dose of cyclosporine on the SD PK of PF-07081532 in otherwise healthy, overweight or obese adult participants.

In vitro data indicate that PF-07081532 is a substrate for the hepatic uptake transporter, OATP1B3. Likewise, an increase in the plasma AUC exposure of PF-07081532 was observed during coadministration of an OATP inhibitor in monkeys. Therefore, a single dose of cyclosporine will be coadministered with PF-07081532 in this study to assess the impact of an OATP inhibitor on the single-dose PK of PF-07081532.

In vitro data also indicate that CYP3A is the predominant CYP isoform contributing to the metabolism of PF-07081532. Therefore, multiple doses of itraconazole will be co-administered with PF-07081532 in this study to assess the impact of a CYP3A strong inhibitor on the single-dose PK of PF-07081532.

PF-07081532 will be administered as a single 40 mg dose in all 3 study periods, and all dosing will be administered with food in order to minimize gastrointestinal related AEs.

Participants will include overweight or obese males and females to represent the target population. Additionally, WOCBP will be permitted with the stipulation that they comply with the contraceptive guidelines provided in [Appendix 4](#).

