6.5.2. Laboratory Data

Laboratory data will be listed and summarized by treatment in accordance with the CaPS.

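### Laboratory abnormalities are counted regardless of baseline in a trial with no untreated period and no scheduled Period 1 post-dose panel, so unchanged pre-dose findings are counted under the cyclosporine or itraconazole combination

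*SAP*

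**What the plan says.** Laboratory abnormalities form part of a secondary endpoint; Protocol section 3 lists "Assessment of TEAEs, clinical laboratory abnormalities, vital signs, body weight, and ECG parameters".

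Under SAP 3.5.2, hematology, chemistry and urinalysis results "will be assessed against the criteria specified in the sponsor", meaning the sponsor's internal reporting standards, whose thresholds are not reproduced. The next sentence begins "The assessment will not take into account whether each participant" and names what is set aside: whether the "baseline test result is within or outside the laboratory reference range for the particular laboratory parameter". The section then defines a laboratory baseline: "The baseline measurement is the latest predose measurement on Day 1 of Period 1".

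SAP 6.5.2 is one sentence: "Laboratory data will be listed and summarized by treatment in accordance with the CaPS". Protocol 9.3.2 adds only that abnormalities of potential concern will be described. Neither document specifies a shift table, a split by baseline status or a count of new or worsened laboratory values. By contrast, SAP 6.5.3 (body weight) and SAP 6.5.5 (ECG) both use change from baseline.

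On design, Protocol 4.2 says "PF-07081532 will be administered as a single 40 mg dose in all 3 study periods". All participants follow one fixed sequence.

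**The concern.** A count that ignores baseline mixes findings present before treatment with findings that arise on treatment. In a trial with a control arm, the background rate in that arm lets the reader allow for the mixture. This trial has no such arm and no untreated period, so the participant's own pre-dose value is the only internal reference. The stated rule does not use it, and no specified laboratory output uses the baseline that SAP 3.5.2 defines.

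What is at stake is the reading of a descriptive safety endpoint. Protocol 2.3.1 lists liver toxicity as a risk for both interacting drugs and kidney toxicity as a risk for cyclosporine. Liver and kidney tests belong to the chemistry panel, which is drawn in both combination periods. A reader of the by-treatment table could not tell a finding that arose under the combination from one brought into the study.

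**Working it through.** The plan gives no figure to reproduce here, so the check sets the texts side by side and adds short arithmetic.

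**1. Where scheduled results can fall.** The safety laboratory row of Protocol Table 1 reads:

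| Time | Safety panel |
|---|---|
| Screening | yes |
| Day -1 | yes |
| Period 1, Days 1 to 5 (PF-07081532 alone) | none |
| Period 2 (with cyclosporine) | cell reads "X (D5 chemistry only" |
| Period 3 (with itraconazole) | yes, before discharge on Day 10 |
| Early termination | yes |

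Scheduled on-treatment results for anyone who completes therefore fall only under the two combinations. An early-termination or unscheduled panel could fall in Period 1, but it would not give a systematic comparison. Period 1 serves as the pharmacokinetic reference but not as a laboratory reference. Because Period 2 is chemistry only, a carried-over hematology or urinalysis finding can appear only under itraconazole; a chemistry finding can appear under both.

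**2. Whether out-of-range values can enter.** Protocol 5.1 requires otherwise healthy participants, and exclusion 23 in Protocol 5.2 sets numeric limits for some tests. It still admits AST or ALT above the upper limit of normal (ULN) but below 1.25×ULN, and total bilirubin above ULN but below 1.5×ULN. Participants with Gilbert's syndrome may exceed the bilirubin limit if direct bilirubin is not above ULN. Hematology and urinalysis have no numeric limit. Whether any of these values meets the sponsor's criteria is unknown.

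**3. Size of one carried-over case.** About 16 participants are enrolled and about 12 complete (Protocol 9.5).

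- Contribution to that test's incidence in a period: 1/16 = 6.3 percentage points, or 1/12 = 8.3 among completers.
- Contribution to a count of new or worsened values: 0.

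**4. Frequency, as illustration only.** Let q be the assumed chance that a participant has a qualifying pre-dose abnormality that persists; the documents give no value. With independent participants, P(at least one case) = 1 − (1 − q)^N, and the expected number among 16 is 16q.

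| q (assumed) | N = 16 | N = 12 | Expected of 16 |
|---|---|---|---|
| 1% | 14.9% | 11.4% | 0.16 |
| 5% | 56.0% | 46.0% | 0.8 |
| 10% | 81.5% | 71.8% | 1.6 |
| 20% | 97.2% | 93.1% | 3.2 |

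The range shows how far the frequency depends on the unseen criteria. The finding rests on steps 1 to 3.

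**5. The baseline definition.** SAP 3.5.2 puts the laboratory baseline before dosing on Day 1 of Period 1. Table 1 schedules no panel that day; the last one before the first dose is on Day -1. Read literally, the definition matches no scheduled sample.

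**The case against.** The strongest reply is that this is an openly stated screening convention. It contradicts nothing in the protocol, it over-counts rather than misses, and it serves a descriptive summary of about 16 people with no hypothesis test. The data will be listed, so each flagged value can be compared with its pre-dose value by hand. Abnormal results that the investigator judges clinically significant, including worsening from baseline, also enter as adverse events under Protocol 10.3.1. The sponsor's standard tables may already show baseline status, and wide thresholds would leave few qualifying pre-dose values.

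Much of this stands, and it limits the weight of the point. It does not correct the reported incidence: listings leave the separation to a later manual reading, and the SAP's explicit sentence points away from a baseline split.

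Two stronger readings are tempting.

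- A reader might apply a flat per-test rate to all 34 hematology, chemistry and dipstick results in Protocol Table 5. With independent tests at 0.5%, 1% or 2%, that gives 16%, 29% or 50% of participants flagged without any drug effect. The documents do not support this. The rates are invented, related tests such as hemoglobin and hematocrit move together, and eligibility limits differ by test. Period 2 has only the 17 chemistry results, for which the same assumptions give about 8%, 16% and 29%.
- A reader might infer that the SAP attributes pre-existing abnormalities causally to the combination. It says only that results are summarized by treatment. SAP 3.5.1 uses attribution language for follow-up adverse events, not for laboratory values.

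**Conclusion.** The point holds as a limited one. The stated rule mixes pre-existing and emergent laboratory abnormalities in a named secondary endpoint, and the design offers no other internal reference to separate them. Each participant with a qualifying, unchanged pre-dose value raises that test's incidence by 6.3 percentage points of 16, or 8.3 of 12, in every combination period where the test is sampled.

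This assumes that the value meets criteria the documents do not show, that it persists until sampling, and that the sponsor's standard output adds no baseline split. The number of such participants cannot be derived. The baseline mismatch between SAP 3.5.2 and the schedule needs none of these assumptions. Both points should be settled before the analysis; neither touches the primary pharmacokinetic comparison.

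**What to change.** 1. In SAP 3.5.2 and 6.5.2, keep the regardless-of-baseline table and add a by-treatment count of new or worsened abnormalities relative to the last value before the first dose, or a shift table. State how worsening is defined.
2. Do not treat a table limited to participants with normal baseline as the emergent one. Someone admitted with ALT slightly above ULN who later rises sharply would be left out of it.
3. In SAP 3.5.2, define the laboratory baseline as the last measurement before the first dose, which under the schedule is the Day -1 panel.

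The cost is one extra table with small cells at 12 to 16 participants. The samples are already planned, and no trial procedure changes.
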